5.2 Exclusion Criteria

Patients who meet one or more of the following criteria will not be considered eligible to participate in the clinical study:

1. Female patients who are breastfeeding or have a positive urine pregnancy test either at the Screening Visit or at Admission.
2. Patients who are unable to eat the prescribed meals during the stay at the site; vegetarian or vegan.
3. Patient has a history of significant drug allergy, as determined by the Investigator.
4. Patient has used a study drug, any prohibited medication(s) (see Section 6.8.2), over-the-counter (OTC) medications, vitamins, dietary and herbal supplements within 14 days or 5 half-lives if known (whichever is longer) prior to the first dose of study drug.
5. Patient has a history of active suicidal ideation in the past 6 months prior to the Screening Visit, or any psychiatric disorders that will affect the patient's ability to participate in the study as determined by the Investigator.
6. Patient has a current or recent (within 14 days prior to the Screening Visit) history of uncontrolled, clinically significant infectious, hematological, renal, endocrine, pulmonary, gastrointestinal, cardiovascular, hepatic, psychiatric, neurologic, or allergic disease.
7. Patient with any of the following laboratory abnormalities either at the Screening Visit or at Admission. These assessments may be repeated once at the discretion of the Investigator.
 - a. Aspartate aminotransferase (AST), alanine aminotransferase (ALT) \geq 2 times the upper limit of normal (ULN)
 - b. Bilirubin \geq 1.5 times ULN
 - c. An estimated glomerular filtration rate (eGFR) according to Cockcroft-Gault \leq 60 mL/min
 - d. Hematology values below the lower limit of normal: Neutropenia, absolute neutrophil count $<$ 1000/mm³, hemoglobin $<$ 9 g/dL, white blood cell $<$ 2.5 \times 10³/ μ L
 - e. Clinically significant abnormalities, as judged by the Investigator
8. Patient has a history of alcohol and/or drug abuse within 24 weeks of the Screening Visit.
9. Patient has positive results for drug testing either at the Screening Visit or at Admission.
10. Patient has positive breath alcohol test either at the Screening Visit or at Admission.

11. Regular consumption of alcohol within 6 months prior to the Screening Visit
(> 7 drinks/week for females, > 14 drinks/week for males where 1 drink = 5 ounces [150 mL] of wine or 12 ounces [360 mL] of beer or 1.5 ounces [45 mL] of hard liquor), or use of drugs of abuse (such as marijuana) within 3 months prior to the Screening Visit.
12. Patient has positive test for hepatitis B surface antigen (HBsAg), anti-hepatitis B core (HBc) antibodies, hepatitis C virus (HCV) antibody, and/or human immunodeficiency virus (HIV) antibody at Screening Visit.
13. Patient has QT interval corrected for heart rate (QTc) using Fridericia's correction (QTcF) > 450 ms for males or QTcF > 470 ms for females either at the Screening Visit or Admission, based on safety 12-lead electrocardiogram (ECG). Patient has Screening or Admission ECG with second- or third-degree atrioventricular block, bundle branch block, arrhythmia (but not sinus arrhythmia or supraventricular premature beats), or illegible QT interval.
14. Patient has history or evidence of cardiopathy, acute coronary syndrome, hypertrophic cardiomyopathy, myocarditis or QT prolongation syndrome.
15. Patient is unwilling to abstain from drinks and foods containing alcohol, grapefruit, or caffeine (including coffee, tea, coke, energy drinks, or chocolate) starting 72 hours prior to the Admission until Day 14 Follow-up Visit.
16. Patient has donated blood or experienced acute blood loss (including plasmapheresis) of greater than 500 mL within 90 days prior to the first dose of study drug.
17. Patients with a known immunodeficiency disorder. Have a history of a major organ transplant or hematopoietic stem cell/marrow transplant.
18. Patients with infections requiring treatment or hospitalization within 14 days prior to the Screening Visit, parenteral antimicrobial therapy within 60 days prior to the Screening Visit, infected joint prosthesis; history of herpes zoster, active herpes simplex, or herpes simplex on suppressive therapy.
19. Patient has a chronic hepatic disease or hepatic impairment.
20. Patient has a history of *Mycobacterium tuberculosis* or positive interferon gamma release assay for tuberculosis (IGRA-TB) or abnormal chest X-ray (for positive IGRA-TB patients) at the Screening Visit.
21. Patient has a history of any lymphoproliferative disorder.
22. Patient has a history of COVID-19 unless fully recovered with no sequelae for 14 days.
23. Patient who had a severe course of COVID-19 (extracorporeal membrane oxygenation, mechanically ventilated).

24. Patient who has recent (within 14 days prior to the Screening Visit or between the Screening Visit and Admission) exposure to someone who has COVID-19 symptoms or positive test result.
25. Patient who has a positive reverse transcription polymerase chain reaction (RT-PCR) test for SARS-CoV-2 either at the Screening Visit or at Admission.
26. Patient who has clinical signs and symptoms consistent with SARS-CoV-2 infection; e.g., fever, dry cough, dyspnea, sore throat, fatigue, or positive SARS-CoV-2 test result within 14 days prior to and including either the Screening Visit or Admission.
27. Patients may not receive any live/attenuated vaccine from 30 days prior to the Screening Visit until Day 14 Follow-up Visit.
28. COVID-19 vaccine should not be given 1 week prior to the Screening Visit.
29. Patients treated with any other medications listed under Inclusion Criteria #9 including all medications listed in Section 6.8.2.
30. Patients with malignancy or history of malignancy except adequately treated or excised non-metastatic basal cell or squamous cell cancer of the skin or cervical carcinoma in situ. Previous treatment with total lymphoid irradiation.
31. History of recurrent inflammatory joint disease other than RA (e.g., gout, Lyme disease) or history of any other autoimmune rheumatic diseases other than Sjogren's syndrome.
32. Major surgery within 30 days prior to the Screening Visit or patients with planned surgery.
33. Patients who have an abnormal chest X-ray for interstitial lung disease (ILD) at the Screening Visit and/or patients with history of ILD.
34. History of fainting or family history of sudden death.
35. Patient has any disorder that would interfere with the absorption, distribution, metabolism or excretion of study drug.
36. Patient has a history of deep vein thrombosis and/or pulmonary embolism.
37. Patient has poor venous access.
38. Patient is an employee of the clinical research team (any Teijin or research site employee) or has a family member who is an employee of these organizations.

39. Patient is unable to understand the protocol requirements, instructions, study related restrictions, nature, scope, and possible consequences of the clinical study. Patient is unlikely to comply with the protocol requirements, instructions and study related restrictions; e.g., uncooperative attitude, inability to return for Follow-up Visits and improbability of completing the clinical study.
40. Patient is judged as inappropriate for study participation by the Investigator for other reasons.

5.3 Lifestyle Considerations

5.3.1 Meals and Dietary Restrictions

Refrain from consumption of grapefruit foods or beverages, or Seville-orange containing foods (e.g., orange marmalade) or beverages from 72 hours before Admission until Day 14.

5.3.2 Caffeine, Alcohol, and Tobacco

1. During each dosing session, patient will abstain from ingesting caffeine- or xanthine-containing products (e.g., coffee, tea, cola drinks, and chocolate) for 72 hours before Admission until Day 14.
2. During each dosing session, patients will abstain from alcohol and alcohol-containing foods, medications, or beverages for 72 hours before Admission until Day 14.
3. Patients who use tobacco products will be instructed that use of nicotine-containing products (snuff, chewing tobacco, cigars, pipes, vaping tobacco products or nicotine-replacement products such as nicotine chewing gum and nicotine plasters) will not be permitted from 1 year before the Screening Visit until Day 14.

5.4 Screen Failures

A screen failure occurs when a patient who consents to participate in the clinical study is not subsequently randomly assigned to study intervention. A minimal set of screen failure information is required to ensure transparent reporting of screen failure patients to meet the Consolidated Standards of Reporting Trials (CONSORT) publishing requirements and to respond to queries from regulatory authorities. Minimal information includes demography, reason for screen failure (e.g., eligibility requirements failed), and documentation of any medical occurrences that qualify as SAEs.

Individuals who do not meet the criteria for participation in this study (screen failure) may be rescreened once. Rescreened patients should be assigned a new patient number for every Screening/Rescreening event.

5.4.1 Screening and Enrollment Log and Patient Identification Numbers

The patient's enrollment will be recorded in the Screening and Enrollment Log.

Upon enrollment, each patient will receive a unique patient identification number. Patient numbers must not be re-used for different patients.

6 Study Intervention(s) and Concomitant Therapy

Study intervention is defined as any investigational intervention(s), marketed product(s), placebo, or medical device(s) intended to be administered to a study patient according to the study protocol.

6.1 Study Intervention(s) Administered

Study drug and study cohorts are summarized in [Table 6–1](#) and [Table 6–2](#), respectively.

Table 6–1 Study Intervention(s) Administered

Intervention Label	TCK-276	Placebo for TCK-276
Intervention Name	TCK-276	Placebo
Intervention Description	TCK-276 or matching placebo is orally administered QD under fed condition in the morning of Day 1 to Day 7.	
Type	Drug	
Dosage Formulation	Tablet	
Unit Dose Strength(s)	10 mg or 25 mg	NA
Dosage Level(s)	10 mg (Cohort 1), 25 mg (Cohort 2), 75 mg (Cohort 3), and 150 mg (Cohort 4) of TCK-276 QD	Matching placebo QD
Route of Administration	Oral	
Use	Experimental	Placebo
IMP or NIMP/AxMP	IMP	
Sourcing	Provided centrally by the Sponsor or locally by the study site, subsidiary, or designee.	
Packaging and Labeling	Study drug will be packaged and labeled in accordance with applicable local and regulatory requirements.	The matching placebo will be packaged and labeled in accordance with applicable local and regulatory requirements.

AxMP = auxiliary medicinal product; IMP = investigational medicinal product; NIMP = non-investigational medicinal product; QD = once daily.

Table 6–2 Study Cohorts

Cohort Title	Cohort 1	Cohort 2	Cohort 3	Cohort 4
Cohort Type	Experimental			
Cohort Description ¹	Patients will receive TCK-276 10 mg QD under fed condition in the morning of Day 1 to Day 7.	Patients will receive TCK-276 25 mg QD under fed condition in the morning of Day 1 to Day 7.	Patients will receive TCK-276 75 mg QD under fed condition in the morning of Day 1 to Day 7.	Patients will receive TCK-276 150 mg QD under fed condition in the morning of Day 1 to Day 7.
Associated Intervention Labels	Investigational drug			

QD = once daily.

1. The first cohort will be divided into 2 subgroups that will consist of 2 sentinel patients (1 active treatment, 1 matching placebo) and 6 patients (5 active treatment, 1 matching placebo) to implement the sentinel dosing approach.

6.2 Preparation, Handling, Storage, and Accountability

TCK-276 tablets are packaged in high density polyethylene (HDPE) bottles containing a desiccant and polyethylene (PE) pharmaceutical coil with polypropylene (PP) caps (30 tablets/bottle). Placebo is provided for to match size, color, and weight of TCK-276 tablets (10 mg or 25 mg).

The Investigator or designee must maintain a log to confirm appropriate temperature conditions (20°C to 25°C [68°F to 77°F]) have been maintained during transit for all study intervention received, and any discrepancies are reported and resolved before use of the study intervention.

Only patients enrolled in the study may receive study intervention, and only authorized site staff may supply or administer study intervention. All study interventions must be stored in a secure, environmentally controlled, and monitored (manual or automated) area in accordance with the labeled storage conditions with access limited to the Investigator and authorized site staff.

The Investigator, institution, or the head of the medical institution (where applicable) is responsible for study intervention accountability and record maintenance (e.g., receipt and final disposition records).

Following completion of the clinical phase of the study and Sponsor review of accountability, all unused supplies will either be returned to the Sponsor (together with the accountability records)

or will be destroyed locally in agreement with the Sponsor and Certificates of Destruction provided to the Sponsor.

Further guidance and information for the final disposition of unused study intervention are provided in the study reference manual or other specified location.

6.3 Measures to Minimize Bias: Randomization and Blinding

Table 6-3 **Measures to Minimize Bias**

Study using IRT	
All patients will be centrally randomized using an IRT. Each patient will be assigned a unique number (randomization number) that encodes the patient's assignment to a treatment group within one of the 4 cohorts of the study, according to the randomization schedule generated by IRT using a validated computer program. Details of the procedure are described in the IRT Manual provided to all sites.
 
Study intervention will be administered/dispensed at the study visits as summarized in the SoA (Table 1-1).
 
Returned study intervention should not be re-dispensed to the patients.

Blind break (IRT)	
This is a double-blind study in which patients/care providers/Investigators/outcomes assessors, are blinded to study intervention. The IRT will be programmed with blind-breaking instructions. In case of an emergency, the Investigator has the sole responsibility for determining if unblinding of a patient's study intervention assignment is warranted. Patient safety must always be the first consideration in making such a determination. If the Investigator decides that unblinding is warranted, the Investigator should make every effort to contact the Sponsor prior to unblinding a patient's study intervention assignment unless this could delay emergency treatment for the patient. If a patient's study intervention assignment is unblinded, the Sponsor must be notified within 24 hours of this occurrence. The date and reason for the unblinding must be recorded.

Blinded study with unblinded third party who is dispensing intervention	
Patients will be randomly assigned in a 3:1 ratio to receive study intervention. Investigators will remain blinded to each patient's assigned study intervention throughout the course of the study. To maintain this blind, an otherwise uninvolved third party will be responsible for the reconstitution and dispensation of all study intervention and will endeavor to ensure that there are no differences in time taken to dispense following randomization.
 
This third party will instruct the patient/patient's LAR to avoid discussing the taste, dosing frequency, or packaging of the study intervention with the Investigator.
 
In the event of a quality assurance audit, the auditor(s) will be allowed access to unblinded study intervention records at the site(s) to verify that randomization/dispensing has been conducted accurately.

--------------------------------------------------------------------------------	---------------------------------------------------------------------------------------------------------------------------------------------------------------------------------------------------------------------------------------------------------------------------------------------------------------------------------------------------------------------------------------------------------------------------------------------------------------------------------------------------------------------------------------------------------------------------------------------------------------------------------------------------------------------------------------------------------------------------------------------------------------------------------------------------------------------------------------------------------------------------------

IRT = Interactive Response Technology; LAR = legally authorized representative.

Sponsor safety staff may unblind the intervention assignment for any patient with an SAE. If the suspected unexpected serious adverse reaction (SUSAR) requires that an expedited regulatory report be sent to one or more regulatory agencies, a copy of the report, identifying the patient's intervention assignment, may be sent to Investigators in accordance with local regulations and/or Sponsor policy.

6.4 Study Intervention Compliance

When patients are dosed at the site, they will receive study intervention directly from the Investigator or designee, under medical supervision. The date and time of each dose administered in the clinic will be recorded in the source documents. The dose of study intervention and study patient identification will be confirmed at the time of dosing by a member of the study site staff other than the person administering the study intervention.

6.5 Dose Modification

The dosing schedule may be adjusted based on the safety and PK results, if necessary, to expand a dosing cohort to further evaluate safety, and/or PK findings at a given dose level or to add cohorts to evaluate additional dose levels. The study procedures for these additional patient(s)/cohort(s) will be the same as that described for other study patients/cohorts.

6.6 Continued Access to Study Intervention After the End of the Study

Study intervention for RA will not continue beyond this study.

6.7 Treatment of Overdose

For this study, any dose of TCK-276 greater than 10 mg (Cohort 1), 25 mg (Cohort 2), 75 mg (Cohort 3), and 150 mg (Cohort 4) within a 24-hour time period will be considered an overdose.

The Sponsor does not recommend specific treatment for an overdose.

In the event of an overdose, the Investigator should:

- a. Contact the Medical Monitor immediately.
- b. Evaluate the patient to determine, in consultation with the Medical Monitor, whether study intervention should be interrupted or whether the dose should be reduced.
- c. Closely monitor the patient for any AE/SAE and laboratory abnormalities until TCK-276 can no longer be detected systemically.
- d. Obtain a plasma sample for PK analysis if requested by the Medical Monitor (determined on a case-by-case basis).
- e. Document the quantity of the excess dose as well as the duration of the overdose.

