4.2 Scientific Rationale for Study Design

This study evaluates the safety, tolerability, and PK of ascending multiple doses of TCK-276 administered as oral tablet(s). The design is standard and is considered appropriate to meet the objectives of this exploratory study.

A double-blind, placebo-controlled study is appropriate and standard for an ascending multiple dose study. This design will minimize bias and provide reference data (i.e., data from placebo-treated patients) which will aid in the interpretation of results. The SRC will review available blinded safety, tolerability, and PK data after each cohort to confirm whether it is safe to proceed with the next planned dose, whether the dose escalation should be stopped, or if the dose should be lowered, repeated or titrated in the subsequent cohort.

The safety assessments for the study are accepted measures for ensuring safety of patients during a clinical study. The PK sampling schedule is considered appropriate given the information available. The justification for dose selection is discussed in Section 4.3.

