4.3 Justification for Dose

In the SAD study, which included dose-levels up to 185 mg (capsule), TCK-276 was generally safe and well tolerated in healthy subjects with no reports of SAEs nor discontinuations due to AEs. The starting dose for the MAD study (10 mg, tablet) is sufficiently lower than the highest dose in the SAD study (185 mg, capsule), and the projected clinical effective dose (75 mg) that was calculated from nonclinical pharmacological study using the rat adjuvant-induced arthritis model.

Patients with RA will be enrolled in this MAD study. Given the data for recently approved RA drugs, an up to 2-fold increased exposure in patients with RA compared to healthy subjects was taken into consideration as a conservative approach. Even if a 2-fold higher exposure in patients with RA would occur, the exposure of the 10 mg in the MAD study corresponds to 20 mg in healthy subjects, which is sufficiently lower than that of the highest dose in the SAD study (185 mg) and the projected clinical effective dose (75 mg).

Therefore, 10 mg as tablet formulation is considered the appropriate starting dose in the MAD study.

The dosing frequency (i.e., QD) was selected considering the PK characteristics of TCK-276 and patient's convenience. The dosing duration (7 days) was considered sufficient to achieve steady state conditions.

Dose Escalation

In this MAD study, the dose escalation progression will be from 10, 25, 75, and up to 150 mg in subsequent cohorts. The overall exposure to TCK-276 (in terms of geometric mean AUC_{tau}) on Day 7 is not expected to exceed the predefined AUC cap [REDACTED]. The exposure at 150 mg dosing in tablet formulation is assumed to be less than the predefined AUC cap based on the results from the SAD study (5 mg to 185 mg, capsule). Therefore, 150 mg is chosen for the highest dose. The dose in Cohorts 2, 3, and 4 may be adjusted based on the safety and PK results from the previous cohorts, if necessary. Dose escalation will only be allowed after blinded assessment of all safety, tolerability, and available PK data up to Day 10 from each previous cohort evaluated by Investigators, Medical Monitor, and Sponsor representatives during the SRC meeting.

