7.1.2 Dose Escalation

After each sub-cohort and cohort, the Principal Investigator and the SRC will evaluate the safety, tolerability data and available PK data up to Day 10 to determine the next dose. The predefined AUC_{tau} [REDACTED] level will be used in the SRC as a benchmark so that the human exposure can be compared with preclinical exposure data. The safety and PK data from all patients in the previous cohort must be reviewed before a decision to escalate the dose can be made. Dose escalation will only occur if data from a minimum of 6 patients have been reviewed from the previous lower dose group, such that data from a minimum of 4 patients who have received active treatment will be used to make the dose escalation decision (based on the randomization of 6 active treatment:2 matching placebo).

Doses will not exceed a dose level at which the geometric mean of AUC_{tau} exceeds or would be anticipated to exceed the following limits:

[REDACTED]

[REDACTED]
[REDACTED]
[REDACTED]
[REDACTED]

If PK data indicate that the predefined AUC [REDACTED] has been achieved or would be exceeded with escalation to the next higher dose, dose escalation will be stopped. A dose in which the stopping criteria have been met will not be repeated and further dose escalation will not occur. Where stopping criteria have not been met, the decision of the SRC may be to give the next intended dose, a smaller than the predefined dose increment, a repeated dose or to stop dosing. The SRC will make the decision for the next dose level (to give the next intended dose, a greater or smaller dose increment than the intended dose, a repeated dose) or whether to stop the study after reviewing all the pertinent safety and any other relevant data and decision of the voting members. If consensus among the voting SRC members cannot be reached then the Principal Investigators, who have the ultimate responsibility for the safety of the patients, will make the final decision on the next dose level or whether to stop the study. In any event, dose escalation can only occur if agreed by the Principal Investigators. The decisions of the SRC on the next dose level will be documented and provided to all the appropriate parties

involved with the study, including the pharmacist to enable study intervention preparation for the next scheduled dosing day.

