1.1		Updated dose strength to 175 mg throughout the document Update the unit of CRP from mg/dL to mg/L, accordingly, SDAI = SJC + TJC +PGA + EGA + 0.1*CRP DAS 28 CRP = $0.56 \times \checkmark$ (TJC) + $0.28 \times \checkmark$ (SJC) + $0.36 \times LN((CRP)+1) + 0.14* \times (PGA) + 0.96$ Added line in section 4.13.8 "If any of the elements are missing, then the corresponding parameter will be considered as missing." to handle the parameter in case of missing elements. Removed inactive URL link of DAS28 ESR	
20	Date of last signature	Final	

LIST OF ABBREVIATIONS

Abbreviation/Acronym	Definition/Expansion	
ACR	American College of Rheumatology	
AE	Adverse event	
Ae	Amount of study drug excreted unchanged in the urine	
AESI	Adverse events of special interest	
ALT	Alanine aminotransferase	
AST	Aspartate aminotransferase	
AUC	Area under the curve	
AUC _{0-inf}	Area under the plasma concentration-time curve from pre- dose (time 0) extrapolated to infinite time	
AUC _{0-t}	Area under the plasma concentration-time curve up to last measurable concentration	
AUC _{tau}	Area under the plasma concentration-time curve over a dosing interval	
BDRM	Blinded data review meeting	
BL	Biostatistician Lead	
BLQ	Below the lower limit of quantification	
BMI	Body mass index	
BP	Blood pressure	
bpm	Beats per minute	
CCL2	C-C motif chemokine ligand 2	
CDAI	Clinical disease activity index	
CI	Confidence interval	
CL/F	Apparent total body clearance, determined for parent only	
Clast	Last observed quantifiable concentration at tlast	
CLr	Renal clearance of drug from plasma	
C _{max}	Maximum plasma concentration determined directly from the concentration-time profile	
COMP	Cartilage oligomeric matrix protein	
CPMS	Clinical Pharmacology, Modeling, and Simulation	

Abbreviation/Acronym	Definition/Expansion	
CS	Clinically significant	
CSR	Clinical Study Report	
Ctrough	Concentration in a dosing period defined as the pre-dose concentration of the day	
CTCAE	Common Terminology Criteria for Adverse Events	
CV	Coefficient of variation	
CXCL10	C-X-C motif chemokine ligand 10	
DAS28	Disease activity score 28	
DRM	Data Review Meeting	
ECG	Electrocardiogram	
eCRF	Electronic case report form	
EGA	Evaluator Global Assessment (Provider global score)	
EOS	End of study	
Fe	Percentage of study drug excreted unchanged in the urine	
Fe%	Urinary cumulative excretion as % of unchanged drug	
GM-CSF	Granulocyte macrophage colony stimulating factor	
HAQ	Health Assessment Questionnaire	
HBc	Hepatitis B core	

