Patients will be admitted to the site from the morning of Day -1 and sequestered for the duration of the treatment (dosing) period. Each patient will receive QD oral doses of either TCK-276 or matching placebo administered as tablets under fed condition in the morning of Day 1 to Day 7. The patients will be discharged on Day 10. The planned dose levels to be tested are 10 mg (Cohort 1), 25 mg (Cohort 2), 75 mg (Cohort 3), and 175 mg (Cohort 4) of TCK-276. Based on the results from the SAD study (5 mg to 185 mg dosing) and the projected clinical effective dose (i.e., 75 mg), 10 mg is selected as the starting dose level in the MAD study. The dose in Cohorts 2, 3, and 4 may be adjusted based on the safety and PK results from the previous cohorts, if necessary. The overall exposure to TCK-276 (in terms of geometric mean area under the plasma concentration-time curve over a dosing interval [AUC_{tau}, tau = 24 hours]) on Day 7 would not be expected to exceed 2,355 ng·h/mL, which is set taking monkey testicular toxicity into consideration.

Dose escalation will only be allowed after blinded assessment of all safety, tolerability, and PK data up to Day 10 from each previous cohort evaluated by Investigators, Medical Monitor, and Sponsor representatives during the Safety Review Committee (SRC) meeting.

Max.

28 days

before

first dose

Day -1

Day 1

Day 2

C

Figure 3-1 Study Design

N = number of patients; PK = pharmacokinetics

Figure 3-2 Study Flow Chart – Multiple Ascending Dose Design

VISIT 1 VISIT 2 VISIT 3 Enrolment Treatment period Followup/End of treatment Informed Admission Randomization Multiple dose Discharge consent and dosing administration Screening period

Day 7

Days 8, 9

Day 10

Day 14

(7 days

after

last dose)

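### Protocol 6.7 fixes the overdose limit at the planned cohort doses, so the limit does not follow a permitted dose change (150 mg limit, 175 mg in the SAP's Cohort 4)

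*Protocol*

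**What the plan says.** Protocol 6.7 defines an overdose, within 24 hours, as "any dose of TCK-276 greater than 10 mg (Cohort 1), 25 mg (Cohort 2), 75 mg (Cohort 3), and 150 mg (Cohort 4"). The four figures are the planned cohort doses of Table 6-1. In the event of an overdose the investigator must call the Medical Monitor at once, decide with the Medical Monitor "whether study intervention should be interrupted or whether the dose should be reduced", follow the patient closely until the drug has cleared, and record the size and duration of the excess.

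Other sections let the dose move:

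- Protocol 4.3, and 4.1 in the same terms: "The dose in Cohorts 2, 3, and 4 may be adjusted based on the safety and PK results from the previous cohorts, if necessary".
- Protocol 4.2 has the SRC consider, after each cohort, "if the dose should be lowered, repeated or titrated in the subsequent cohort".
- Protocol 6.5 allows the schedule to be changed "to add cohorts to evaluate additional dose levels".
- Protocol 7.1.2 lists among the SRC's options "a smaller than the predefined dose increment, a repeated dose or to stop dosing". Its next sentence on the options also names a greater increment.

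The SAP has Cohort 4 at 175 mg. Section 3.1 states that the "planned dose levels to be tested are 10 mg (Cohort 1), 25 mg (Cohort 2), 75 mg (Cohort 3), and 175 mg" for Cohort 4. The revision history for SAP version 1.1 shows that the change was deliberate: "Updated dose strength to 175 mg throughout the document".

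**The concern.** An overdose limit should be tied to the dose a patient is meant to receive. The limit in 6.7 is tied to the dose that was planned before the first cohort was treated. The two agree only while no cohort's dose changes.

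Once a dose changes, the limit can misclassify in either direction. After an increase, correct dosing meets the definition of overdose and attracts the 6.7 steps. After a reduction or a repeat, a patient can receive more than intended and still fall outside the definition, so those steps are not required. The second direction matters more for safety, because it would follow a cautious SRC decision and because the amounts that escape include the originally planned dose, a foreseeable dosing error after a change. What is at stake is safety handling and its documentation, not a statistical result.

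**Working it through.** **Inputs.** Overdose limits: protocol 6.7. Planned doses: protocol Table 6-1. SAP doses: SAP 3.1 and 4.2.1. Allocation of 6 active and 2 placebo per cohort, and dosing once daily on Days 1 to 7: protocol 4.1.

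**Step 1: the plan's own figures.** A correctly given dose is flagged if it is greater than the limit.

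| Cohort | 6.7 limit (mg) | Protocol dose (mg) | SAP dose (mg) | SAP dose flagged? |
|---|---|---|---|---|
| 1 | 10 | 10 | 10 | No |
| 2 | 25 | 25 | 25 | No |
| 3 | 75 | 75 | 75 | No |
| 4 | 150 | 150 | 175 | Yes |

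At the protocol's planned doses each limit equals the dose and nothing is flagged. The text is consistent until a dose moves.

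**Step 2: upward change (the case in the SAP).** Excess over the limit: 175 - 150 = 25 mg, and 25/150 = 16.7%. Scheduled active doses in the cohort: 6 patients x 7 days = 42, so 42 of 42 are flagged. This assumes a full cohort with no dropouts or replacements. Placebo patients take no TCK-276 and cannot meet the definition, but investigators are blinded (Table 6-3) and could not tell which of the eight patients do.

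**Step 3: lowered or repeated dose (permitted, not shown to have occurred).** Suppose a cohort repeats the previous planned level. The largest 24-hour total that is not counted equals the printed figure, since a total equal to the limit is not greater than it. The ratio is printed figure / repeated dose:

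- Cohort 2 repeating 10 mg: 25/10 = 2.5 times the intended dose.
- Cohort 3 repeating 25 mg: 75/25 = 3.0 times.
- Cohort 4 repeating 75 mg: 150/75 = 2.0 times.

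So if Cohort 4 repeated 75 mg, a patient given the dose twice in one day would total 150 mg and would not be counted.

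**Step 4: added cohort.** Section 6.7 gives figures for Cohorts 1 to 4 only. Section 6.5 says that added cohorts follow the same study procedures, so the overdose steps carry over, but there is no figure to trigger them.

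**Step 5: after the fix.** With the limit set at the assigned dose, the Cohort 4 limit at 175 mg is 175 mg, and 0 of 42 correct doses are flagged. In Step 3 any total above the repeated dose is counted.

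**The case against.** The best answer is that the 6.7 figures simply restate the planned doses, that 4.1 and 4.3 say those doses may be adjusted, and that sites would read overdose as exceeding the cohort's dose. That is probably how it would work in practice. The Medical Monitor is a core SRC member (10.1.5), so the first 6.7 step would be a call to someone who took part in the dose decision. Under 7.1.2 that decision is documented and sent to all parties concerned, including the pharmacist. Much of the extra monitoring overlaps with confinement to Day 10 and follow-up to Day 14. The 42 doses therefore count an effect of wording, not 42 harms.

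On the missed-excess side, a second member of staff confirms each dose (6.4), the SAP lists compliance in mg (4.8.2), and signs or sequelae of a suspected overdose are adverse events in any case (10.3.1). Overdose alone is not an AE or SAE unless it is an intentional overdose with possible self-harm intent. The escaping totals of 25, 75 and 150 mg are below the 185 mg reported as well tolerated in the single-dose study, although that was a single capsule dose in healthy subjects.

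Finally, the record may be incomplete. The SAP cites protocol version 3.0 in Section 1 but version 2.0 in 3.2.2, and it still describes sentinel dosing in every cohort, which the supplied protocol limits to Cohort 1. The SAP is dated September 2023 and protocol version 3.0 December 2022, so an amendment in between could have changed 6.7.

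All of this limits the consequence, and it holds the point to minor. It does not make the text right. Sections 4.1 and 4.3 give the doses with an adjustment clause, 6.7 gives them without one, and nothing in the supplied documents overrides 6.7. The dose check reduces errors but does not classify those that occur.

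**Conclusion.** Minor, and wrong as written. The overdose limit does not move with the dose. On a literal reading it flags all 42 scheduled active doses in the SAP's Cohort 4, each 25 mg (17%) above the limit. It would also miss a true excess of up to 2.0 to 3.0 times the intended dose if a cohort repeated the previous planned level. Only the first case appears in the documents; the lowered, repeated and added-cohort cases are permitted possibilities. Cohort 1 is not among the adjustable cohorts and is unaffected.

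Three stronger readings are tempting, and the documents do not support them.

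- A reader might infer that 175 mg is itself an error or breaks a ceiling, since 4.3 names 150 mg as the highest dose. But 4.3 allows the Cohort 4 dose to be adjusted, and 7.1.2 allows a greater increment within the AUC limits. The documents do not say who chose 175 mg or why, so it cannot be called unauthorised; equally, that it was an SRC decision is an inference.
- A reader might infer that patients were overdosed, or that the 6.7 steps were in fact triggered. Nothing supplied shows this.
- A reader might infer that the results are compromised. No endpoint, analysis set, sample size or stopping rule uses the overdose definition, and neither document plans an overdose summary.

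The conclusion assumes that 6.7 as supplied was in force when 175 mg was given, which cannot be confirmed from these documents.

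**What to change.** In protocol 6.7, replace the four fixed figures with one rule: an overdose is any amount of TCK-276 taken within 24 hours that exceeds the dose assigned to the patient's cohort. The assigned dose is 10 mg for Cohort 1. For Cohorts 2 to 4 and any added cohort it is the planned dose or, where changed, the SRC-approved dose documented under 7.1.2.

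The cost is one sentence. The SRC record it refers to is already required. Doses, sample size, analyses, AUC limits and the 6.7 steps themselves stay as they are. If a later amendment has already made this change, nothing further is needed.
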